7.1 Schedule of Assessments

This is an observational study. Therefore, no study-specific visits are scheduled in the protocol.

Investigators (i.e., paediatricians and/or endocrinologists) who treat at their clinics short children who were born SGA will be responsible for screening and enrolling subjects. Eligible subjects (see also section 5.3.1) include subjects who completed or permanently discontinued treatment with Saizen® or other r-hGH products within 5 years prior to enrolment in the study. Subjects may have been enrolled in previous sponsored clinical studies with r-hGH in the SGA indication or may have received r-hGH products in a post-marketing setting. In any case, subjects (with parents/guardian as applicable) will need to attend first a screening visit in order to sign the ICF and enrol in the study.

During the course of the study, subjects are not required to visit the study Investigator. Subjects may go to their GP or other treating physician for their routine medical visits. Only information gathered by the treating physician/GP from procedures performed as part of the routine clinical practice may be available for the study. The medical data of interest (see Table 1) for this study (when/if available) will be collected by the investigator from the patient's treating physician/GP. Since the treating physician/GP will document the subject's routine medical data considered necessary for the patient's standard medical care, not all the data of interest described in Table 1 may be available to the study Investigator.

In order to minimize the subject loss to follow-up and to maintain subject motivation during the 10 years of the follow-up study, the CRO's dedicated PMC will contact the subjects once a year to update/confirm subjects' and treating physicians' contact information in order to send them the "Yearly Subject and Investigator SALTO kits", and to identify any change in health status/medical history. If any relevant change is identified by the PMC, the PMC will notify the investigator, who will gather the pertinent information from the treating physician/GP. The detailed content of the "Yearly Subject SALTO kit" is addressed in section 10.1.

In order to ensure adequate collection of the post-treatment medical data of interest, the following activities will be performed:

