- After every yearly call from the PMC, the PMC will update the contact information of the subject and subject's treating physician in the appropriate databases, and send the "Yearly Subject SALTO kit" to the subject/contact person. In addition, the PMC will identify any relevant change on the subject's health status, and will contact the Investigator who will obtain the relevant medical data from the subject's treating physician as previously described.
- 2. The subject can request a copy of his/her medical history/laboratory results from the treating physician/GP and send it to the Investigator who will enter the information into the electronic case report form (eCRF).
- 3. The Investigator will call the subject 5 and 10 years after r-hGH discontinuation to obtain any additional available relevant medical information.

Data collection will start once subjects have entered the study and will continue for a maximum of 10 years after discontinuation of treatment with Saizen® or other r-hGH products. Prior to collecting any data, the Investigator (i.e. paediatrician/endocrinologist) will ensure that the subject has provided a signed, written ICF according to the procedure described in section 9.2.

For subjects who have entered the study within the 5-year period after r-hGH treatment discontinuation, any data of interest occurring from the time of permanent cessation of r-hGH therapy up to the signature of the ICF will be retrospectively collected and recorded into the eCRF by the Investigator.

Data reporting is allowed at any time if a subject or his/her Investigator reports an adverse event related to changes in glucose metabolism parameters or to malignancy or to any Serious Adverse Event related to r-hGH treatment.

During subsequent follow-up visits, the Investigator or subject's treating physician/GP (when applicable) will ensure that the subject is informed and updated on the study.

Method of Reporting AEs of Interest

At the time of obtaining Informed Consent, the Investigator will explain the process of reporting an AE to the subject. The subject will be provided with a leaflet containing information on the AEs of interest (i.e., type 2 diabetes mellitus, metabolic syndrome and/or changes in glucose metabolism parameters, fasting insulin levels, HbA_{1c}, 2-hour OGTT results, blood pressure, lipid parameters, and parameters related to malignancies) and key message/information of the Company's post-approval commitment (PAC).

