If the subject experiences an AE of interest (see definition of AE of interest in section 7.4.1.1) or a serious adverse event (SAE) of interest, the subject or his/her parents/guardians will be asked to call the PMC on the toll-free phone number that is enclosed in the yearly Subject SALTO Kit. The subject will inform the PMC of the AE/SAE details and the contact information of the treating physician. Upon receipt of the information, the PMC will immediately forward the received information to the corresponding Investigator. The Investigator may follow up with the subject and the subject's physician to confirm the received medical information, and determine if the AE/SAE is relevant for this study. This will be followed by reporting the AE/SAE of interest to the CRO/Sponsor by completing an eCRF and an SAE Report Form in case of SAE.

The timelines and methods for reporting these AEs/SAEs of interest by the Investigator are described in section 7.4.1.2.

Table 1 Summary of Data to be Collected*

Time points	Baseline	At any time over 10 years	At year 5	At year 10
Demographic characteristics and r- hGH treatment history	х			
Medical history/relevant change in medical history	х	х	х	х
Familial medical history/ relevant change in familial medical history	Х	х	Х	Х
Anthropometric parameters				
Height (cm)	X	X	X	X
Weight (kg)	X	X	X	Х
Waist circumference (cm)	Х	Х	Х	X
Hip measurement (cm)	Х	Х	Х	X
Occurrence of type 2 diabetes/ glucose metabolism disorders/ metabolic syndrome	х	х	Х	х
Occurrence of malignancies (type, histological result, histological result, location, size, grading, severity, treatment, outcome)	x	х	x	х
Metabolic parameters				
Fasting Plasma insulin	Х	Х	X	х
Fasting Plasma glucose	Х	Х	Х	Х
HbA1c (%)	Х	Х	X	Х
2 hour OGTT	Х	Х	Х	Х
Plasma triglycerides	Х	Х	X	Х
HDL-cholesterol	Х	χ	Х	Х
LDL-cholesterol	Х	Х	Х	Х
Total cholesterol	Х	Х	Х	Х
Blood pressure	Х	Х	Х	Х
Urinary albumin excretion rate	Х	Х	Х	Х
Urinary Albumin:creatinine ratio	Х	Х	Х	Х
Concomitant medications (Only relevant concomitant medications are to be collected as per the Investigator's judgement)	х	х	х	х

^{*} Data to be collected by the Investigator only if available during routine medical care performed by the treating physician/GP

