7.4.3 Laboratory Assessments

No scheduled laboratory assessments are required by protocol. Nevertheless, laboratory data of interest related to glucose metabolism, metabolic syndrome or any malignancy (see Table 1)

deemed necessary and requested by the treating physician/GP as part of the subject's standard medical care, will be, when available, recorded into the eCRF by the Investigator (see section 7.1).

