8.3 Endpoints

8.3.1 Primary Endpoints

The number and proportion of subjects diagnosed at any time during the 10-year follow-up will be tabulated for the two primary endpoints:

- Type 2 diabetes mellitus
- Any malignancy

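### The diabetes endpoint measures diagnosed type 2 diabetes only: retained subjects who were never tested count as non-events, and subject-time is credited whether or not their status was known

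*Protocol*

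**What the plan says.** **Source of the data.** Protocol 7.1 states: "Only information gathered by the treating physician/GP from procedures performed as part of the routine clinical practice may be available for the study". It concedes that "not all the data of interest described in Table 1 may be available to the study Investigator". The Table 1 footnote repeats the limit: "Data to be collected by the Investigator only if available during routine medical care performed by the treating physician/GP". Section 7.4.3 adds: "No scheduled laboratory assessments are required by protocol".

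**Active contacts.** The CRO's patient management centre calls each subject yearly, partly "to identify any change in health status/medical history". In addition, "The Investigator will call the subject 5 and 10 years after r-hGH discontinuation to obtain any additional available relevant medical information". Subjects can also report events of interest by telephone and send in their own records.

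**Endpoint and analysis.** Section 8.3.1: "The number and proportion of subjects diagnosed at any time during the 10-year follow-up will be tabulated for the two primary endpoints". Section 8.4 admits to the safety population every included subject with at least one r-hGH administration for short stature due to SGA. Section 8.5.2 adds an incidence rate whose subject-time starts at the last r-hGH treatment and stops when the 10-year period is over. Section 8.7 keeps dropouts who had an event, removes event-free dropouts from later analyses, and excludes the subject-years analysis from this rule.

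**The concern.** None of these sections separates a subject known to be free of diabetes from one whose status was never assessed. The calls and self-reports pass on diagnoses that somebody has already made. They test nobody, so they cannot reveal undiagnosed disease. A subject who stays in contact for 10 years without a single glucose, HbA1c or OGTT value enters the proportion as a non-event and the rate with full person-time.

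The study is a post-approval commitment on diabetes and malignancy risk. Its objective speaks of occurrence of type 2 diabetes, and 8.5.1 promises an estimate of its incidence. There is no control group that might share the same under-ascertainment. If the result is read as total incidence, missed cases make it look more reassuring than it is. The mechanism concerns the diabetes endpoint; glucose testing has no bearing on malignancy.

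**Working it through.** **Inputs from the protocol.** Up to 35% attrition over 10 years, about 300 enrolled and 200 wanted at year 10 (8.1). The planned figure reproduces: 200 × 1.5 = 300; dividing by retention gives 200/0.65 = 308; and 300 × 0.65 = 195. Only the 35% is used below.

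**Inputs not in the protocol.** It gives neither a diabetes risk nor a testing rate. The following are assumptions: true 10-year risk p = 3%; share of subjects ever tested q = 0.3 to 0.9; share of untested cases diagnosed anyway s = 0 or 0.5; constant hazards of event and dropout.

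**Step 1: under-ascertainment alone, no dropout.** If testing is unrelated to risk, the detected share of cases is c = q + (1−q)s, and the observed proportion is p × c.

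| q | s = 0 | s = 0.5 |
|---|---|---|
| 0.3 | 0.9% (ratio 0.30) | 1.95% (0.65) |
| 0.5 | 1.5% (0.50) | 2.25% (0.75) |
| 0.7 | 2.1% (0.70) | 2.55% (0.85) |
| 0.9 | 2.7% (0.90) | 2.85% (0.95) |

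The ratio does not depend on p. If higher-risk subjects are tested more often, the share of cases tested exceeds q and the loss is smaller.

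**Step 2: adding the 8.7 dropout rule.** With 10λ = −ln(0.97) = 0.0305 and 10μ = −ln(0.65) = 0.4308, the share of subjects whose event precedes dropout is E = λ/(λ+μ) × (1 − exp(−10(λ+μ))) = 0.0660 × 0.3695 = 0.0244. Retained non-events are n = 0.65 × (1−p) + 0.65 × (1−c) × p. The reported proportion is cE/(cE + n).

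- c = 1: 0.0244/(0.0244 + 0.6305) = 3.7%, or 1.24 × truth, with about 196 of 300 in the denominator
- c = 0.8: 0.0195/(0.0195 + 0.6344) = 3.0%, about equal to truth
- c = 0.65: 2.4% (0.81 × truth)
- c = 0.5: 1.9% (0.62 × truth)
- c = 0.3: 1.1% (0.375 × truth)

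The ratios are nearly the same at true risks of 1% and 5%. The two effects cancel near 80% detection: below it the proportion is too low, above it too high.

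**Step 3: subject-time.** Taken literally, 8.5.2 gives everyone 10 years. At 35% dropout with constant hazard, mean actual follow-up is 0.35/0.0431 = 8.1 years. Dividing by 10 instead of 8.1 understates the rate by about 19% (1 − 8.1/10), in addition to any missed diagnoses. The 8.7 rule does not offset this, because it is not applied to subject-years.

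**The case against.** - **The endpoint says diagnosed.** For diagnosed diabetes, an undiagnosed subject is correctly a non-event. This stands: the shortfall is against total incidence only. But 8.5.1 and the objectives use the broader terms, so the report needs to say which quantity it gives.
- **A reader might infer that the reported incidence is biased low overall, because never-tested people sit in a denominator of all subjects.** The protocol does not support that. Section 8.7 removes event-free dropouts and keeps dropouts with events, which raises the proportion. With more than about 80% of cases detected, the net error is upward.
- **Ascertainment is wider than routine records.** True: the yearly calls, the telephone line, subject-supplied records and the year-5 and year-10 calls capture known diagnoses. They do not find undiagnosed ones.
- **Missing counts are already planned.** Section 8.5.3 reports non-missing and missing numbers for each quantitative secondary variable, which include glucose, HbA1c and OGTT. That answers much of the transparency worry. It does not show how many subjects had any of these tests, and it is not tied to the primary endpoint.
- **This belongs in the SAP.** An assessed-subjects analysis often does, and the SAP was not available, so its absence from the protocol is not in itself a fault. What stands is what the protocol itself fixes: the analysis set, the subject-time definition and the missing-data rule. Together they treat unknown status as no event with full time. A SAP can add a denominator but cannot supply tests that were never done.

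**Conclusion.** The point holds in a limited form. Undiagnosed type 2 diabetes among retained subjects counts as a non-event, and 8.5.2 credits time regardless of when status was last known. The primary result is therefore the incidence of diagnosed diabetes and, through this mechanism, understates total diabetes incidence.

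The size cannot be read from the protocol. The ratios of 0.30 to 0.95 rest on assumed values of q and s and on testing being unrelated to risk. The net direction of the reported proportion is not established, because the separate 8.7 rule works the other way (about 1.24-fold at 35% dropout). The rate is in a different position: the literal subject-time definition lowers it by about 19% at 35% dropout under constant hazard, and the 8.7 rule does not counter that.

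**What to change.** In Protocol 8.5.2:

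1. State that the quantity estimated is the incidence of diagnosed type 2 diabetes.
2. Report how many subjects had at least one glucose, HbA1c or OGTT value by year 5 and by year 10.
3. Add a sensitivity analysis of diabetes incidence among subjects ever assessed. Label it as probably too high if testing follows risk, and not as a guaranteed bound.
4. For the diabetes rate, end subject-time at the earliest of first event, last contact at which diabetes status was ascertained (counting the yearly call and the year-5 and year-10 calls), or 10 years.

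Optionally, have the existing yearly call record diabetes diagnosis and diabetes testing as yes/no items.

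No visit or laboratory test is added, so the observational design is unchanged. The cost is a few tables and a caveat on selective testing. That caveat also applies to item 4: cases are always ascertained, so cutting time mainly from subjects of unknown status can push the rate up. Counting the calls as ascertainment limits this. The 8.7 dropout rule is a separate matter and needs its own correction.

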7.2 Demographic and Other Baseline Characteristics

Demographics, subject's medical history (including age at starting treatment with r-hGH, r-hGH product(s) used, start and stop dates for each r-hGH product used, age at treatment end/permanent discontinuation of r-hGH treatment, duration of r-hGH treatment, maximum dose, clinically significant AEs experienced during r-hGH treatment) and subject's familial medical history will be collected for all subjects and entered into the eCRF by the investigator. For subjects who have

entered the study within the 5-year period after r-hGH treatment discontinuation, baseline characteristics will be comprised of the demographics, subjects' medical history and familial medical history corresponding to the end of r-hGH treatment.

Additional measurements at baseline for this study are as described in section 7.1.

7.3 Assessment of Efficacy

No efficacy parameters are being assessed during this study.

7.4 Assessment of Safety

Safety will be assessed through the recording, reporting and analysis of AEs. Specific safety endpoints (i.e., AEs of interest) will be measured as per study's primary and secondary objectives described in section 4.

The Investigator should report any AE of interest (that may be serious or non-serious, related or unrelated to r-hGH treatment) as described in section 7.4.1.1, whether observed by the Investigator or subject's physician or reported by the subject. Serious Adverse Events of interest and other SAEs assessed as related to r-hGH treatment by the investigator should be reported to the Sponsor as described in section 7.4.1.2 and 7.4.1.4.

The methods of reporting, recording and assessing AEs of interest are described in section 7.4.1.2. The reporting period for the AEs of interest is described in section 7.4.1.3.

7.4.1 Adverse Events

7.4.1.1 Adverse Event Definitions

Adverse Events (AEs)

An AE is any untoward medical occurrence in a subject or clinical investigation subject administered a pharmaceutical product, which does not necessarily have a causal relationship with this treatment. An AE can therefore be any unfavourable and unintended sign (including an abnormal laboratory finding), symptom, or disease temporally associated with the use of the Investigational Medicinal Product (IMP), whether or not considered related to the IMP.

In this particular study, the following AEs of interest should be reported to the sponsor:

• Type 2 diabetes mellitus, glucose metabolism disorders other than overt type 2 diabetes mellitus, such as abnormal fasting or postprandial glycaemia, abnormal 2-hour OGTT or increased insulin levels or any other component of metabolic syndrome defined by the WHO as insulin resistance + at least two of the following criteria: a) High blood pressure (>=140 mm Hg systolic or >=90 mm Hg diastolic) or taking blood pressure medication, b) Plasma triglycerides >=150 mg/dL (>=1.7 mmol/L); c) HDL cholesterol <35 mg/dL (<0.9 mmol/L) in men or <39 mg/dL (1.0 mmol/L) in women; d) BMI greater than 30 and/or waist:hip ratio >0.9 in men, >0.85 in women; e) Urinary albumin excretion rate >=20 μg/min or albumin:creatinine ratio >=30 mg/g (18).

Any malignancy.

In this particular study only the AEs of interest, which can be assessed by the investigator as related or unrelated to the previously received r-hGH treatment, should be reported to the Sponsor.

It is important to remark that the pre-defined AEs of interest for safety monitoring of this study are defined as the primary and secondary objectives which are described in section 4 (see also Table 1).

In cases of surgical or diagnostic procedures, the condition/illness leading to such a procedure is considered as the AE rather than the procedure itself.

In case of a fatality, the cause of death is considered as the AE, and the death is considered as its OUTCOME.

The Investigator is required to grade the severity/intensity of each AE.

Investigators will reference the National Cancer Institute - Common Terminology Criteria for Adverse Events (CTCAE), version 3.0 (publication date: 9 August 2006). This is a descriptive terminology that can be used for AE reporting.

If a particular AE's severity/intensity is not specifically graded by the guidance document, the Investigator is to revert to the general definitions of Grade 1 through Grade 5 and use his or her best medical judgment.

The 5 general grades are:

Grade 1: Mild

Grade 2: Moderate

Grade 3: Severe

Grade 4: Life-threatening or disabling

Grade 5: Death related to AE

Note: Death (Grade 5 as defined by NCI-CTCAE version 3.0) is mainly regarded as an *outcome*, to be documented as described below.

According to the Sponsor's convention, if a severity/intensity of Grade 4 or 5 is applied to an AE, then the treating physician must also report the event as an SAE (see definition below) as per section 7.4.1.4.

The Investigator must also systematically assess the causal relationship of AEs of interest in relation to previous r-hGH treatment, by using the following definitions (the decisive factor being the temporal relationship between the AE and administration of the IMP):

Probable: A causal relationship is clinically/biologically highly plausible and there is a plausible

time sequence between onset of the AE and administration of the Investigational

Medicinal Product and there is a reasonable response on withdrawal.

Possible: A causal relationship is clinically/biologically plausible and there is a plausible time

sequence between onset of the AE and administration of the Investigational Medicinal

Product.

Unlikely: A causal relationship is improbable and another documented cause of the AE is most

plausible.

Unrelated: A causal relationship can be definitively excluded and another documented cause of

the AE is most plausible.

Abnormal Laboratory Findings and Other Abnormal Investigational Findings

Abnormal laboratory findings and other abnormal investigational findings (e.g. on an electrocardiogram [ECG] trace) should not be reported as AEs unless they are associated with clinical signs and symptoms or are considered otherwise medically important by the Investigator or general practitioner. If an abnormality fulfils these criteria, the identified medical condition (e.g. anaemia, increased ALT) must be reported as the AE rather than the abnormal value itself.

Serious Adverse Events (SAEs)

In this particular study, the SAEs assessed by the Investigator as related to the previously received r-hGH treatment, and the SAEs of interest, should be reported to the sponsor.

An SAE is any untoward medical occurrence that at any dose:

- Results in death
- Is life-threatening

NOTE: The term "life-threatening" in this definition refers to an event in which the subject is at risk of death at the time of the event; it does not refer to an event that hypothetically might cause death if it were more severe.

- Requires inpatient hospitalization or prolongation of existing hospitalization
- Results in persistent or significant disability/incapacity
- Is a congenital anomaly/birth defect
- Is otherwise considered as medically important

Important medical events that may not result in death, be life-threatening, or require hospitalization may be considered as SAEs when, based upon appropriate medical judgment, they may jeopardize the subject or may require medical or surgical intervention to prevent one of the outcomes listed in this definition. Examples of such events include allergic bronchospasm requiring intensive treatment in an emergency room or at home, blood dyscrasias or convulsions that do not result in inpatient hospitalization, or the development of drug dependency or drug abuse.

For the purposes of reporting, any suspected transmission of an infectious agent via a medicinal product is also considered a serious adverse reaction and all such cases should be reported in an expedited manner as described in section 7.4.1.4.

Events that Do Not Meet the Definition of an SAE

Hospitalisation for routine check-up should not be reported as a SAE. However, all events leading to unplanned hospitalizations or unplanned prolongation of an elective hospitalization (e.g., undesirable effects of any administered treatment) must be documented and reported as SAEs.

Events Not to Be Considered as AEs/SAEs

Medical conditions present at study start, that do not worsen in severity or frequency during the study are defined as Baseline Medical Conditions, and are NOT to be considered AEs.

